### Specific Aim 1: Anorectal pathophysiology of LARS patients

Objective: use fecobionics to obtain physiological and pathophysiological signatures of anorectal function in a heterogeneous group of LARS patients. Based on the epidemiology and symptomatology of LARS, it is expected that the heterogeneous group will contain an almost equal number of LARS patients with incontinence, frequency and urgency, and those primarily with constipation and feelings of incomplete emptying. Due to the spread (heterogeneity) in the patient group regarding symptoms, regression analysis will be the primary statistical tool to associate symptoms with experimental findings. We will also compare to age- and sex-matched healthy controls from already conducted studies.

Milestone: Describe the mechanosensory signature, variation of the measured variables, and computed endpoints in LARS patients.

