## **Research Design and Methods**

The overall goal of this proposal is outlined in the specific aims section. Specifically, we will target anorectal diagnostics of LARS patients to be conducted in the Department of Surgery at Prince of Wales Hospital in Hong Kong. In both studies listed below, we aim to recruit a heterogeneous group of patients to allow us to assess the effect of several underlying risk factors. In both studies, we will study the patients after closure of defunctioning stoma as we deem it impossible to carry out anorectal functional studies in patients with low rectal cancer before their rectal cancer surgery and assessing anorectal function post LAR before defunctioning stoma closure will produce unreliable, irrelevant data.

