### Data collection:

Patients will be assessed at baseline and following will be recorded for all patients:

- Demographic data
- Body Mass Index (BMI)
- Significant Past Medical and Surgical History
- Obstetric History (female patients only)
- Rectal Cancer stage: TNM staging, location of tumour from anal verge on preop image

- Rectal Cancer treatment
  - o Neoadjuvant chemoradiotherapy/radiotherapy/chemotherapy
  - o Surgery – Open/Laparoscopic/Robotic/TaTME, level of anastomosis
  - o Post-operative complications
  - o Postop chemotherapy / radiotherapy
  - o Timing of defunctioning stoma (ileostomy / colostomy) closure
- LARS questionnaires: to assess Quality of life associated with LARS (Figure 4)

All patients will undergo the following tests:

- Integrated Fecobionics anorectal test (see clinical workflow below)
- High Resolution Anorectal Manometry (ARM) to assess resting and squeeze pressures, sensitivity, rectal capacity and recto-anal inhibitory reflex.
- Conventional balloon expulsion test
- Defaecography

Clinical data will be recorded and stored electronically in the hospital server. Completed questionnaires will be recorded and entered into database software and stored in the hospital server.

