### **Study design related to specific *Aim 1*: Anorectal pathophysiology of LARS patients**

Studies are planned to include a heterogeneous group of LARS patients with a broad scale of symptoms. We will study 30 patients recruited from a pool of postoperative patients who are under the care of our Department. The department has a large cohort of patients with LARS and it is anticipated that it will be easy to recruit the patients.

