**Data analysis including statistics and sample size determination.**

A number of biomechanical parameters will be computed from the recorded data. These parameters include but are not limited to:

- Pressure difference between the rear and front ends (a measure of anal sphincter relaxation and key to the determination of phases of the defecatory process)
- Orientation and bending of Fecobionics for assessment of the anorectal angle

- Velocity of expulsion (as measured from the time difference between sensor data)
- Tension
- Strain (deformation) and displacement

Definitions of tension, strain and displacements can be found in the two books by the [name]. Sensory measures and clinical data will be related statistically to the mechanical measures. Endpoint data will be expressed as mean±SD if they can be considered normally distributed. Significance of the differences between two methods will be evaluated by ANOVA where appropriate and by multiple and single regression analysis. The results will be considered statistically significant when p<0.05 (2-tailed). Multiple regressions will be used to evaluate risk factors using causal and predictive analysis. Repeatability and distribution will be determined based on coefficient of variation (SD/mean) and used to evaluate accuracy.

The projected number of subjects, n, required to test a null hypothesis is given by the following equation:

$$n > \left[ \frac{[Z_{2\alpha} + Z_{2\beta}] \sigma}{\delta} \right]^2$$

where  $\alpha$  is the required probability of a Type I error,  $\beta$  is the required probability

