of a Type II error,  $\delta$ , is the estimated difference between the means of two comparison groups, and  $\sigma$  is the estimated standard deviation of the means in each of the two comparison groups. We assume  $2\alpha < 0.05$  ( $Z_{2\alpha} = 1.96$ ) and  $2\beta < 0.10$  ( $Z_{2\beta} = 0.84$ ). We assume the values of mean difference, d, and standard deviation, s, from previous experience in the clinical laboratory and from reported data in the literature on the involved patient groups and the sensitivity and specificity of current tests. An alternative method is to use sample size estimation based on the Altman-Bland analysis (<http://wwwusers.york.ac.uk/~mb55/meas/sizemeth.htm>). Preliminary data on expulsion time using BET and Fecobionics were used in the sample size analysis. Data variation (SD, SE) was computed for preliminary data. The confidence interval for the 95% limits of agreement was computed and n was determined. For both analyses, given the exploratory nature of the study, we consider a heterogeneous group of patients and that 80% of operated patients will develop LARS. Using these boundaries and criteria, we arrived at a sample size of 30 in the Aim 1 study for evaluation of statistical significance, association and risks. Though the material may be too small to account for confounders, we will obtain clear indications of risks and causes. For the comparison with previously studied subjects, we have a pool of 35 healthy asymptomatic subjects, 20 patients with FI and 15 patients with constipation to compare with.

**Clinical Assessments of device safety:** Fecobionics have now been used in more than 70 human studies without any incidents or adverse effects. In addition, a safety study has been performed in 12 pigs without any device related issues or damage to anorectal mucosa (yet unpublished data). Since Fecobionics is still an experimental device, we will pay attention to safety. If any safety issue occurs, it will be characterized and reported. Additional data obtained will include procedural duration, sensation

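### The planned risk-factor regressions in 30 patients have no safeguard against overfitting, so noise alone can yield a well-fitting model or a false risk factor

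*Combined protocol and SAP*

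**What the plan says.** Under Specific Aim 1, "regression analysis will be the primary statistical tool to associate symptoms with experimental findings". Research Design and Methods says that a heterogeneous group is recruited "to allow us to assess the effect of several underlying risk factors". The section on data analysis and sample size adds: "Multiple regressions will be used to evaluate risk factors using causal and predictive analysis". The only inferential rule is "The results will be considered statistically significant when p<0.05 (2-tailed").

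The Aim 1 design section gives the number: "We will study 30 patients recruited from a pool of postoperative patients who are under the care of our Department". The sample-size text ties that number to the same purpose: "we arrived at a sample size of 30 in the Aim 1 study for evaluation of statistical significance, association and risks". It calls the study exploratory and concedes that the sample may be too small to deal with confounders. The same sentence nevertheless expects the data to point clearly to risks and causes.

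The variables recorded at baseline are listed under Data collection. They include demographics, stage, neoadjuvant treatment, surgery ("Open/Laparoscopic/Robotic/TaTME, level of anastomosis"), complications, postoperative therapy and stoma closure. No section says which of them enter a regression, how many may enter, how they are chosen, or how the fit is to be checked.

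**The concern.** With 30 patients and a long list of candidates, least squares fits noise. A model can show a large R-squared, or keep a variable at p<0.05, when nothing on the list is related to the outcome. Regression is the declared primary tool and one of its stated uses is prediction, so the point bears on the main output of the study.

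This is a different problem from confounding, which is the only limitation the plan concedes. Overfitting occurs even when every candidate is independent of the others and of the outcome. At stake is whether a reported set of predictors of bowel dysfunction would reproduce in the next group of patients.

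**Working it through.** **Step 1: the plan's own figure.** The stated formula is n > [(1.96 + 0.84)σ/δ]². The plan gives no values for δ and σ: "We assume the values of mean difference, d, and standard deviation, s, from previous experience in the clinical laboratory". The figure of 30 therefore cannot be reproduced. It follows if δ/σ is about 2.80/√30 = 0.51. A ratio of 0.4 gives 49, 0.5 gives 32 and 0.6 gives 22. The alternative basis is limits of agreement for expulsion time. Neither basis concerns a model with several predictors.

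**Step 2: count the candidates.** The list is under Data collection; the coding is my assumption, shown as a range.

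| Item | Coarse | Expanded |
|---|---|---|
| Demographics (age, sex) | 2 | 2 |
| BMI | 1 | 1 |
| Medical and surgical history | 1 | 2 |
| Obstetric history (women only) | 1 | 1 |
| Stage and tumour height | 2 | 4 |
| Neoadjuvant treatment | 1 | 3 |
| Surgical approach and anastomosis level | 2 | 4 |
| Complications | 1 | 1 |
| Postoperative therapy | 1 | 2 |
| Stoma closure timing and type | 1 | 2 |
| **Total** | **13** | **22** |

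That is 30/13 = 2.3 down to 30/22 = 1.4 patients per term. The Fecobionics, manometry, balloon expulsion and defecography measures come on top.

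**Step 3: all terms in one model.** With no true association and normal errors, R-squared for p terms follows Beta(p/2, (n−1−p)/2), with mean p/(n−1). With n = 30:

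| Terms p | Mean R-squared, p/29 | 95th percentile | P(R-squared > 0.5) |
|---|---|---|---|
| 3 | 0.10 | 0.26 | 0.00 |
| 10 | 0.34 | 0.56 | 0.11 |
| 13 | 0.45 | 0.66 | 0.34 |
| 20 | 0.69 | 0.87 | 0.93 |
| 22 | 0.76 | 0.92 | 0.98 |

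Simulation of 2,000 noise data sets with 20 terms gave mean R-squared 0.69, mean adjusted R-squared −0.01 and median out-of-sample R-squared about −2.2. At least one coefficient had p<0.05 in 39% of data sets. The overall F test rejected in 5.4%, close to its nominal level.

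**Step 4: forward selection at p<0.05.** With m independent noise candidates, the chance that at least one is kept is close to 1 − 0.95^m: 0.49 for m = 13, 0.60 for m = 18 and 0.64 for m = 20. Simulation agrees: 48% to 49% for 13, about 60% for 18, and 63% to 65% for 20, depending on the run. With 18 candidates, mean apparent R-squared is about 0.28 among data sets where something is selected. Over all data sets it is 0.17, because about 40% select nothing and count as zero.

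**The case against.** The strongest reply is that the plan does not describe a 20-term model. The Data collection list says what is recorded, not what is modelled. The analysis section speaks of regressions in the plural and also of single regressions, so several small models fit the text at least as well as one saturated model. That stands. A reader might infer that the analysis as planned will explain most of the symptom variation from noise; the documents do not support this. At the coarse count of 13 terms the expected null R-squared is 0.45, and under selection the apparent fit is lower still.

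Second, R-squared is not mentioned anywhere; the yardstick is p<0.05, and the overall F test keeps its level. A reader might infer that an inflated R-squared will be published as evidence of prediction. That is a forecast about reporting which the documents do not make. The p<0.05 rule brings its own problem, however, when it is applied to individual coefficients or used for selection, as steps 3 and 4 show.

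Third, the risk-factor sentence names no outcome, so taking symptoms as the outcome is partly an assumption. The null results above do not depend on which outcome is used.

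Fourth, the study is called exploratory and its small size is acknowledged. This softens the point but does not settle it. The acknowledgement covers confounders only, brings no safeguard, and sits beside an expectation of clear evidence on causes.

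**Conclusion.** The point holds in a conditional form. The plan commits to predictive and causal multiple regression in 30 patients without any protection against overfitting, and both obvious routes through its variable list are unreliable. Entering the listed terms together gives an expected noise R-squared of 0.45 to 0.76. Forward selection from 13 to 20 of them keeps a false risk factor in about 50% to 63% of noise data sets. Because the plan neither requires nor excludes these models, its results can mislead; it does not follow that they will.

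The figures rest on the 13-to-22 count, which is mine and not the plan's, on complete data for all 30 patients, and on no true association. Missing data, or obstetric history entered for women only, would reduce n and raise the null R-squared. The selection figures also assume independent candidates. Correlated ones, such as tumour height and anastomosis level, would be expected to lower the false-selection rate somewhat. The mean p/(n−1) does not depend on that correlation as long as no term is redundant.

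**What to change.** Before analysis, add the following to the statistical section:

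- For each multiple regression, name the outcome and at most two or three predictors, chosen by the sponsor. Expected null R-squared is then 2/29 = 0.07 or 3/29 = 0.10. Alternatively, use ridge regression on the full list.
- For any model presented as predictive, report R-squared corrected for optimism by bootstrap or leave-one-out, with any selection or tuning repeated inside each resample.
- Show the remaining factors as single-variable estimates with confidence intervals, labelled exploratory, and do not sort them into risk factors and others by p<0.05.
- Replace the sentence that expects clear evidence on risks and causes with hypothesis-generating wording.

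This needs no extra patients or tests, only some wording and a few lines of code. The price is that reported predictive performance will be lower and fewer factors can be examined jointly.

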### **Clinical Work Flow for the integrated device.**

This section pertains to the procedures related to use of Fecobionics. All tests prior to Fecobionics are done per department standards. The patient is instructed about the tests. The integrated device is calibrated in a one-step procedure. Similar to the conventional expulsion test, the device is placed in the rectum by manual insertion with the person lying on the side. The bag is distended with simultaneous recording of symptom level until urge to defecate. Volume is recorded. When the urge level is reached, the patient will move to the toilet chair for attempting to expel it. The patient will report sensory data. Most patients who do not suffer from constipation will be able to expel it within 1-2 minutes. If the patient fails to expel the device by himself, the physician or nurse can, if deemed necessary, pull it out by traction of a tiny thread attached to the front end (like the thread used for tampons). The thread is 50 cm long so even if the device relocates to the left side of the colon, it can still gently be pulled out. In the worst case, an endoscope can be used to pull it out.

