**Exclusion Criteria:**

1. Patients who are not willing to undergo the specified tests in this study
2. Pregnant women

The studies on LARS patients will focus on pathophysiological studies where we describe the expulsion characteristics, with focus on anal canal opening related to rectal mechanosensory data and to changes in the anorectal angle during defaecation. We will study expulsions at the urge-to-defecate level for the patients and we will correlate to data obtained by conventional technologies and to patient characteristics such as age, and symptoms as well as to risk factors. The study subjects will also be tested with conventional expulsion testing, defecography, rectal bag distension, and ARM. The studies will determine endpoints of clinical value such as expulsion time and velocity, maximum angle difference, pressure signatures and geometry changes.

**Expected Results and Milestones:** The expected outcome is that the device will perform as shown in the previous human experiments (n>60) where no adverse effects have been recorded. We anticipate successful access in LARS patients with no device-related adverse events or device malfunctions. Completion of the study is expected to derive outcome measures reflecting the defecatory function as the major impact.

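### SD/mean is to determine repeatability and evaluate accuracy, but with the one Fecobionics test per patient that is specified it shows only between-patient spread, and it never measures accuracy

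*Combined protocol and SAP*

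**What the plan says.** All places are in the combined protocol and SAP.

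- **Statistic.** *Data analysis including statistics and sample size determination*: "Repeatability and distribution will be determined based on coefficient of variation (SD/mean) and used to evaluate accuracy". It does not say whether the SD is within or between patients.
- **Number of tests.** *Data collection* has patients assessed at baseline and lists the Fecobionics test once. *Clinical Work Flow for the integrated device* describes one insertion and one filling, then: "When the urge level is reached, the patient will move to the toilet chair for attempting to expel it". No replicate, number of repeats or retest interval is given. The text after the exclusion criteria speaks of expulsions in the plural, for patients in the plural, with no number per patient.
- **Population.** *Specific Aim 1* and its study design section call for a heterogeneous group with a wide range of symptoms.
- **Method comparison.** "Significance of the differences between two methods will be evaluated by ANOVA where appropriate and by multiple and single regression analysis". The text after the exclusion criteria adds: "we will correlate to data obtained by conventional technologies".
- **Sizing.** After a formula for a difference in means, the same data analysis section continues: "An alternative method is to use sample size estimation based on the Altman-Bland analysis"; "Preliminary data on expulsion time using BET and Fecobionics were used in the sample size analysis"; "The confidence interval for the 95% limits of agreement was computed and n was determined". Limits of agreement are not mentioned in the planned analysis.

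**The concern.** Repeatability asks how far two readings on the same patient differ. Accuracy asks how far a reading lies from a reference. With one reading per patient, SD/mean mixes true differences between patients with measurement error, and it contains no reference value.

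The direction of a misreading matters here. *Technological background* expects Fecobionics to reduce variation, and the Aim 1 milestone includes the variation of the measured variables. Under the sentence as written, a lower SD/mean could be reported as better repeatability and accuracy, when it might only mean that the device separates patients less.

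A smaller gap concerns agreement. Limits of agreement for BET and Fecobionics expulsion time contributed to the sample size, but the analysis text names only ANOVA, regression and correlation. As planned, the report need not say how far the two expulsion times differ in an individual patient.

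**Working it through.** **Inputs from the documents:** n = 30; two-sided 5% significance; one Fecobionics test per patient as described; SD/mean as the statistic; limits of agreement for BET and Fecobionics expulsion time as one sizing route. The coefficients of variation (CVs), correlations and numbers of pairs below are illustrative assumptions, because the documents give no such values.

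**1. The plan's own figure.** The sample size of 30 can be neither confirmed nor refuted. The printed formula gives 30 if δ/σ is about 0.512: ((1.96 + 0.84)/0.512)² = 29.9. The limits-of-agreement route gives 30 if the accepted 95% CI half-width of a limit is about 1.96√(3/30) = 0.62 SD of differences. Neither target is stated.

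**2. Repeatability.** With one value per patient, SD/mean = √(patient CV² + error CV²). The 95% repeatability coefficient, as a fraction of the mean, is 1.96 × √2 × error CV.

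| Patient CV | Error CV | SD/mean | Sampling range, n = 30 | Repeatability coefficient |
|---|---|---|---|---|
| 30% | 10% | √(0.09 + 0.01) = 31.6% | 23% to 41% | 28% |
| 10% | 30% | √(0.01 + 0.09) = 31.6% | 23% to 41% | 83% |

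The sampling range is the 2.5 to 97.5 percentile of 200,000 simulated normal samples. The planned statistic cannot tell the two cases apart. In general, an observed SD/mean of c fits any error CV from 0 to c. The degrees of freedom for within-patient error are 30 × (1 − 1) = 0.

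**3. Accuracy.** Multiply every reading by 1.5: the SD becomes 1.5 SD, the mean becomes 1.5 mean, and the ratio is unchanged. A device reading 50% too high therefore has the same SD/mean as a correct one. This does not depend on the number of tests.

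**4. If repeats are intended.** Two tests in m patients give m degrees of freedom for the within-patient SD. The exact 95% limits are √(m/χ²) times the estimate:
- m = 30: √(30/46.98) = 0.80 to √(30/16.79) = 1.34.
- m = 10: √(10/20.48) = 0.70 to √(10/3.247) = 1.75.

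**5. Correlation does not supply limits of agreement.** The critical r at n = 30 is 2.048/√(28 + 2.048²) = 0.361. With equal SDs, the SD of differences is √(2(1 − r)) between-patient SD.
- r = 0.361: 1.130, so the limits are bias ± 1.96 × 1.130 = ±2.2 SD.
- r = 0.8 (p < 0.001): 0.632, so ±1.24 SD.
- If one method's SD is 0.7 of the other's, r = 0.361 gives 1.96√(1 + 0.49 − 2 × 0.361 × 0.7) = ±1.94 SD of the more variable method.

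**6. Precision of the added analysis**, in SDs of differences. The limit half-width is 1.96√(3/n); the mean-difference half-width is t/√n.

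| Pairs | Each limit | Mean difference |
|---|---|---|
| 30 | ±0.62 | ±0.37 |
| 24 (20% lost, assumed) | ±0.69 | ±0.42 |
| 15 (50% lost, assumed) | ±0.88 | ±0.55 |

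Some loss of pairs is foreseeable. *Specific Aim 1* expects almost half the group to be mainly constipated, and *Potential Pitfalls and Alternative Strategies* provides for a device that is not expelled. The documents give no rate.

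**The case against.** **Repeats may be intended.** The plural expulsions after the exclusion criteria is the closest wording to more than one run, and the word repeatability itself may imply repeats. This stands as far as it goes: repeats are not excluded. But no number is stated, and the accuracy problem remains with any number.

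**SD/mean has a proper use.** The sentence also names distribution, for which it is a legitimate description. This stands, and the fix keeps that use.

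**Agreement is not the study's aim.** Aim 1 seeks physiological signatures and their association with symptoms. The study is described as exploratory, n = 30 is justified for significance, association and risks, and the existing tests are described as imperfect surrogates. This largely stands, which is why the limits of agreement are an inexpensive addition and not the main correction. Against it, the protocol calls comparison with reference technologies important and says the device may replace current tests.

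**ANOVA could cover it.** A paired ANOVA would give the mean difference and a residual from which limits could be derived. But the model is not stated, and there is no plan to report them.

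**The limits would be impure.** The BET uses a 50 ml balloon, while the Fecobionics bag is filled to urge, so the difference combines device and volume. The limits would also cover only patients who expelled both. Both points are true and must be stated with the result.

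A reader might infer that the plan means to treat a significant correlation as agreement. The documents do not say so; the point is only that correlation and regression do not supply the limits.

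**Conclusion.** The point holds for the repeatability and accuracy sentence and should be fixed. With one value per patient, as the protocol describes, SD/mean carries no separate information on within-patient error: the same 31.6% is compatible with repeatability coefficients of 28% and 83% of the mean. That non-identifiability is algebra. The particular CVs are illustrative and do not measure harm in this trial. The accuracy part needs no assumption about the number of tests.

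The agreement part is a secondary gain, resting on the protocol's own use of limits of agreement in sizing.

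Two wider readings are not supported. Nothing here undermines Aim 1's primary symptom regressions or shows that the sample size is wrong. Nor is the missing rule for non-expulsion a separate finding here; it matters as a condition on whom the limits of agreement describe.

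**What to change.** **Main change.** Replace the sentence with: *Between-patient variation will be described by SD, and by SD/mean for positive-valued measures.* Delete the use for evaluating accuracy. Delete repeatability unless repeat tests are already intended. If they are, state how many patients are tested and how often, and report the within-patient SD with a CI.

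**Addition.** For expulsion time, BET versus Fecobionics:
- Report the paired mean difference and 95% limits of agreement with CIs among patients who expelled both devices, on the log scale if differences grow with the mean.
- Give the number of pairs, and show non-expulsions in a separate paired expelled/not-expelled table.
- State that the limits describe expellers only, that they combine device and volume effects, and that each is imprecise.

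**Cost.** SAP wording plus a routine paired analysis of data already planned, with no added patients, visits or tests. The protocol gives up a repeatability and accuracy claim, or must specify repeats it already intends. The paired table is imprecise too: if 24 of 30 patients (80%) had the same result with both devices, the Wilson 95% CI would be 63% to 90%.
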